8.0 Efficacy Analyses

8.1 General Considerations

All efficacy analyses will be conducted using the FAS. Unless otherwise specified, each elagolix dose group will be compared to placebo. All statistical tests will be conducted at an alpha level of 0.1 (two-sided). A test will be deemed significant if the P value rounded to three decimal places is less than or equal to 0.1 unless otherwise specified.

Unless otherwise specified, categorical data will be summarized by frequencies and percentages for each treatment group and overall; continuous data will be summarized by the mean, standard deviation, median, minimum, and maximum for each treatment group and overall. For the analyses of change from baseline, the within-group changes will be summarized with the mean, standard deviation, and the median; between-group differences will be summarized with the mean, standard error, P value, and the 90% CIs.

Baseline refers to the last non-missing value obtained prior to or on Study Day 1.

8.2 Handling of Missing Data

Missing data will be imputed using the following methods for the efficacy analyses:

Mixed-Effect Model Repeat Measurement (MMRM): The repeated measures analyses will be conducted using mixed models including observed measurements at all visits. The mixed model includes the categorical fixed effects of treatment, visit and treatment-by-visit interaction, subject as a random effect, and the continuous fixed covariates of baseline measurement. An unstructured variance covariance matrix will be used. Parameter estimation is based on the assumption of data being missing at random and using the method of restrictive maximum likelihood (REML). Missing data will not be imputed for MMRM analysis.

Observed Cases (OC): The OC analysis will not impute values for missing evaluations, and thus a subject who does not have an evaluation on a scheduled visit will be excluded from the OC analysis for that visit. OC will exclude values after a subject prematurely discontinues from study drug.

Multiple Imputation (MI): The MI approach will be used as a sensitivity analysis for the primary endpoint. For the primary endpoint, 20 'complete' datasets will be generated using SAS PROC MI. The seed will be 123. Using the Cochran-Mantel-Haenszel (CMH) model adjusted for FG score ($< 8, \geq 8$) and normal/obese status ($BMI < 30, \geq 30$) at Baseline, the imputed endpoints will be analyzed using each of the 20 datasets. SAS PROC MIANALYZE will be used to generate the final inferences of difference of proportion of menstrual cycle responders between each elagolix group and placebo.

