Beginning at Screening and throughout the Treatment Period, each subject will complete an electronic daily bleeding diary. The subjects will also undergo weekly blood draws for progesterone levels. A progesterone level  $\geq$  3 ng/mL will be used to indicate ovulation.

Subjects will undergo procedures and activities as listed in the Activities Schedule at the 30-day post-treatment follow-up visit. An unscheduled visit may occur when the subject returns to the clinic at any time for the evaluation of symptoms, changes in concomitant medications, or any AEs.

The study schematic is presented in Figure 1. Further details regarding study procedures are located in the Operations Manual (Appendix F). See Section 5 for information regarding eligibility criteria. Study sites and subjects will remain blinded for the duration of the study.

Figure 1. Study Schematic

BID = twice daily; M = month; PTFU = post-treatment follow-up; QD = once daily

Some of the study visits and visit activities (including but not limited to clinical laboratory tests and concomitant medication assessment) may be conducted in the home or non-hospital/clinic environment by qualified individuals at the investigator's request and with the subject's agreement where local regulation allows.

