3.3 Other Efficacy Endpoint(s)

The primary and secondary efficacy endpoints are listed in Section 3.1 and Section 3.2, respectively. The additional efficacy endpoints are:

- Proportion of complete menstrual cycle responders (normal menstrual cycles by the beginning of Month 3 and maintained thereafter each month through Month 6).
- Change from Baseline in the LH serum AUC at each scheduled assessment during the Treatment Period.
- Change from Baseline in the FSH serum AUC at each scheduled assessment during the Treatment Period.
- Change from Baseline in total and free testosterone serum concentration at each scheduled assessment during the Treatment Period.
- Number of menstrual bleeding episodes during the Treatment Period.
- Number of ovulations based on weekly serum progesterone level during the Treatment Period.
- Proportion of subjects with at least 2 ovulations during the Treatment Period
- Endpoints related to hyperandrogenism – Patient Global Impression (PGI) for both acne and hirsutism; change from Baseline at each scheduled assessment during the Treatment Period for the following: acne measured with total lesion

count and investigator's global assessment (IGA), hirsutism measured with Ferriman–Gallwey (FG) score.

- Endpoints related to metabolic features - change from Baseline at each scheduled assessment during the Treatment Period for the following: glycated hemoglobin (HbA1c), fasting insulin/glucose, body mass index (BMI), lipids, waist circumference.
- Change from Baseline at each scheduled assessment during the Treatment Period for additional hormones: androstenedione, anti-Mullerian hormone (AMH), estradiol (E2), progesterone.
- Change from Baseline in ovarian volume at each scheduled assessment during the Treatment Period.
- Endpoints related to the subject's quality of life: change from Baseline in domains from the Polycystic Ovary Syndrome Questionnaire (PCOSQ) (emotions, body hair, weight, infertility problems, and menstrual problems) and the Menstrual Bleeding Questionnaire (MBQ) at each scheduled assessment during the Treatment Period.

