8.4 Secondary Efficacy Analyses

The key secondary endpoint is change from baseline in the area under the luteinizing hormone (LH) serum concentration-time curve over the 4 hours (area under the curve [AUC]) at Day 7. Serial blood samples for LH assay will be collected at Baseline and Weeks 1, 4, and 16 according to the following schedule: 0 hour, 0.5, 1, 1.5, 5, 2.5, 3, 3.5, and 4 hours. The AUC over the 4 hours will be calculated based on the linear trapezoidal rule.

The analysis for the key secondary endpoint will be based on a mixed-effects model with repeated measures (MMRM). If appropriate, the natural logarithmic transformation or other transformation may be employed for LH AUC. The MMRM analysis will include the fixed categorical effects of treatment, visit, treatment-by-visit interaction, baseline FG score ($< 8, \geq 8$), and baseline normal/obese status ($\text{BMI} < 30, \geq 30$), subject as a random effect, and the continuous fixed covariate of baseline LH AUC. Each elagolix dose group will be compared to the placebo group; the LS mean of treatment difference and associated 90% CI and p-value will be reported.

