8.5.2 LH, FSH, testosterone and other hormones

The changes from baseline to each scheduled assessment of the hormone parameters will be analyzed using a mixed-effects model with repeated measures (MMRM). If appropriate, the natural logarithmic transformation or other transformation may be employed for the hormone parameters. The MMRM analysis will include the fixed categorical effects of treatment, visit, treatment-by-visit interaction, baseline FG score ($< 8, \geq 8$), and baseline normal/obese status ($\text{BMI} < 30, \geq 30$), subject as a random effect, and the continuous fixed covariate of baseline hormone value.

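### The MMRM pairs a redundant random subject effect with an unstructured matrix; for weekly progesterone that matrix has 300 parameters, with no small-sample correction or fallback structure

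*SAP*

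**What the plan says.** SAP 8.2 defines the MMRM for the efficacy analyses: "The mixed model includes the categorical fixed effects of treatment, visit and treatment-by-visit interaction, subject as a random effect", plus the baseline value as a covariate. It then adds: "An unstructured variance covariance matrix will be used". Estimation is by REML, assuming data missing at random.

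SAP 8.4, for the key secondary endpoint, lists "subject as a random effect, and the continuous fixed covariate of baseline LH AUC". SAP 8.5.2, for the hormones, lists "subject as a random effect, and the continuous fixed covariate of baseline hormone value". Both add the FG and BMI strata, and neither restates the covariance matrix.

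Section 8.5.2 fits each hormone's change from baseline at all of its scheduled visits. SAP 3.3 includes progesterone among the "additional hormones: androstenedione, anti-Mullerian hormone (AMH), estradiol (E2), progesterone". Protocol 4.1 says "The subjects will also undergo weekly blood draws for progesterone levels", and the activity schedule (Protocol Appendix D; Operations Manual 2.2) places progesterone at every week from 1 to 24. Progesterone is not in the ANCOVA list of SAP 8.5.5, so 8.5.2 is the section that governs its change from baseline.

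No section names a degrees-of-freedom method, a small-sample correction of the standard errors, or a covariance to fall back on if the model does not converge.

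**The concern.** There are two separate issues.

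First, the model in 8.2 specifies within-subject correlation twice. A random subject effect with independent residuals is one model (compound symmetry), and an unstructured residual matrix is another. Together they contain one variance that the data cannot determine. When the software reports this, the analyst must drop one of the two, and the SAP does not say which. The two resulting models can give different standard errors. Protocol 7.1 leaves the sponsor unblinded throughout, so this choice should not wait for the data.

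Second, the rule in 8.2, applied to a weekly series, produces a very large covariance matrix for a trial of 130 women. Plain model-based standard errors treat the estimated matrix as known. With many covariance parameters and missing weeks, that can make intervals too short.

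**Working it through.** **Inputs.** N = 5 × 20 + 30 = 130 women in 6 groups (SAP 2.4). The stated power of at least 85% reproduces: 88.9% by pooled chi-square for 50% against 10%, 20 against 30 women, two-sided alpha 0.05. LH AUC has 3 post-baseline visits, Weeks 1, 4 and 16 (SAP 8.4). Progesterone has 24. Efficacy tests use two-sided alpha 0.1 (SAP 8.1). The documents state no covariance-parameter count.

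**Redundancy.** Let R be the unstructured matrix, J the matrix of ones and s the subject variance. The marginal covariance is V = R + sJ. Replacing R by R + cJ and s by s − c leaves V unchanged, so s cannot be separated from R. With T visits there are T(T+1)/2 + 1 parameters, but only T(T+1)/2 dimensions:

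| Outcome | T | Parameters | Rank |
|---|---|---|---|
| LH AUC, FSH AUC | 3 | 6 + 1 = 7 | 6 |
| Testosterone, E2 | 6 | 21 + 1 = 22 | 21 |
| Progesterone | 24 | 300 + 1 = 301 | 300 |

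The ranks were confirmed numerically. The estimated contrasts and their model-based standard errors depend on the covariance parameters only through V. They are the same with or without the redundant term.

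**Key secondary model.** Three visits, unstructured matrix, no correction:
- 25% stopping early plus 5% intermittent missing, 300 trials: reported SE divided by true SE 1.02, 1.00, 0.99; non-coverage of nominal 90% intervals 9.5 to 10.9%.
- 25% plus 10%, 400 trials: 1.01, 1.00, 1.01; false positives 9.5 to 10.4%.

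No bias is visible.

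**Weekly progesterone.** Covariance parameters: 24 × 25 / 2 = 300. Treatment-by-visit means: 6 × 24 = 144. The runs below use an unstructured REML fit without the random effect and with uncorrected standard errors.

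Light missingness, normal data, covariance 0.4 + 0.6 × 0.6^lag, missing completely at random; SE ratios at Weeks 1, 13 and 24:
- Complete data, 300 trials: 0.97, 1.02, 1.01.
- 10% stopping, 5% intermittent, 500 trials: 0.99, 1.00, 0.99.
- 25% stopping, 5% intermittent, 600 trials: 0.99, 0.99, 0.98.

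Non-coverage was 9.9 to 11.2% against 10%. The fits settled within 56 iterations.

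Heavier missingness, 25% stopping early and 10% intermittent:

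| Run | Week 1 | Week 13 | Late weeks | Late false positives, nominal 10% |
|---|---|---|---|---|
| 160 trials, covariance as above | – | – | 0.327/0.339 = 0.96 (Week 24) | 11.3% |
| Pure AR(0.6) | – | about 0.95 (mid-period) | about 0.96 (Week 24) | 11.6 to 12.3% (late and mid-period) |
| 450 trials per covariance | about 0.99 | 0.97 to 0.99 | 0.92 to 0.95 (Weeks 21 to 24) | 12 to 14% |
| 600 trials, two covariances | 1.02 to 1.03 | 0.94 to 0.97 | 0.93 to 0.94 (Week 24) | 12.7 to 13.3% |

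**Monte Carlo error.** Two dose contrasts sharing placebo correlate at (1/30)/(1/30 + 1/20) = 0.4. With five contrasts pooled, the relative error of a ratio from R trials is about 0.5 × √[2(1 + 4 × 0.4²)/(5R)]. That is 2.3% for R = 300, 1.7% for R = 600 and 3.2% for R = 160. The light-missingness shortfalls cannot be told from zero. The 6 to 7% shortfall at Week 24 in 600 trials can.

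**Pattern.** The shortfall grows with follow-up and with missing weeks. This fits the mechanism: when a visit is fully observed, its contrast rests almost entirely on that visit's own data, and cross-visit covariances matter only when values are missing.

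**The case against.** A reader might infer that the standard errors are too small because the model is not identifiable. That does not follow. Only the split between s and R is undetermined, and V is not. The shortfall above appears in a model without the random effect, so it is a separate matter.

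A reader might also infer that the key secondary analysis is compromised. The redundant variance and a probable warning are real there, but with 6 covariance parameters the treatment estimates are unique and the simulations show no bias.

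A shortfall of 10% is tempting too. One run of 160 trials at the heavier missingness, with its within-subject covariance not stated, gave 0.329/0.365 = 0.90 at Week 24 and 13.9% false positives. It lies beyond the larger runs and should not be taken as the size of the effect.

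The strongest defence is that little depends on this. The primary endpoint uses CMH. Progesterone change is one of many additional endpoints, and SAP 8.5.4 analyses the weekly series as ovulations, by ANCOVA and CMH. SAP 10.0 disclaims Type I error control. All of that stands and limits the point to moderate importance. It does not remove the specification error from the key secondary model.

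It could also be said that the unstructured matrix was meant for the random effects. The SAP does not say so, and a single subject effect has one variance, so there would be nothing to leave unstructured. If two readings are possible, the text still needs correcting.

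**Conclusion.** The point holds in two limited parts.

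1. The random subject effect is redundant beside the unstructured matrix wherever 8.2 applies, including the key secondary LH AUC model. The consequence is practical: a foreseeable singular Hessian or convergence warning, and an unplanned choice of model by an unblinded sponsor. Contrasts and standard errors are not altered by the redundancy itself.

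2. For weekly progesterone, the uncorrected unstructured model gives standard errors about 0 to 2% short under light missingness. At late visits they are about 4 to 8% short under 25% early stopping plus 10% intermittent missing, with false-positive rates of about 11 to 14% at nominal 10%. Early visits show little or no shortfall.

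The second part depends on assumed missingness rates and within-subject correlations, since the documents give neither. Heavier missingness was not evaluated. The redundancy and the counts of 300 and 144 need no such assumptions.

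**What to change.** - In SAP 8.2, 8.4 and 8.5.2, delete the random subject effect and state that the unstructured matrix is the within-subject residual covariance across visits.
- Name Kenward-Roger standard errors and degrees of freedom for every MMRM.
- For weekly progesterone, pre-specify a more parsimonious covariance, for example heterogeneous Toeplitz with 24 variances + 23 correlations = 47 parameters, or an ordered list of structures to try if the unstructured fit does not converge. Either keeps every scheduled visit in the endpoint.

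Limiting the progesterone model to the 4-weekly visits (6 visits, 6 × 7 / 2 = 21 parameters) would also work. It changes the endpoint stated in Protocol 3.4 and SAP 3.3, however, so it is a trade-off and not just a wording change.

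The cost is a few lines of SAP text and slightly wider intervals. A structured covariance adds an assumption about how correlation decays over weeks. Neither Kenward-Roger nor the Toeplitz model was simulated here, so the size of the improvement is not quantified.

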8.3 Primary Efficacy Endpoint(s) and Analyses

8.3.1 Primary Efficacy Endpoint(s)

The primary efficacy endpoint is the proportion of menstrual cycle responders.

A subject is considered as a menstrual cycle responder if she has at least 2 normal menstrual cycles during the final 4 months of the Treatment Period. For subjects who complete the treatment period this will be Month 3 to Month 6; for subjects who prematurely discontinue at Month X, where X is greater than or equal 4, this will be Month (X – 3) to Month X; for subjects who prematurely discontinue at Month X, where X is less than 4, this will be Month 1 to Month X. A normal menstrual cycle will be defined as follows:

- a. Subject has menstrual bleeding (excluding spotting only) AND
- b. The length of the menstrual cycle is from 21 to 35 days. Menstrual cycle length is defined as the length of time from the first day of one menstrual bleeding episode to the day before the next menstrual bleeding episode (calculated by [first day of the next menstrual bleeding episode] minus [the first day of the referenced bleeding episode]).

A menstrual bleeding episode is defined with the following rules:

- a. A bleeding episode requires at least one of the following:
 - At least 2 consecutive days of bleeding, OR
 - At least 1 day of bleeding followed immediately by 1 day of spotting or 1 day of missing data then spotting or 1 day of missing data then bleeding, OR
 - At least 1 day of spotting followed immediately by 1 day of bleeding or 1 day of missing data then bleeding.
- b. Consecutive days of spotting only with no days of bleeding are not considered as an episode.
- c. If consecutive days of spotting are adjacent to a day with bleeding, then these consecutive days with spotting are counted as part of the same bleeding episode.
- d. One day of missing data between a spotting day and bleeding day or between 2 bleeding days qualifies as part of the same bleeding episode.

Examples are presented in [Table 1](#).

Table 1. Examples of Menstrual Bleeding Episodes

Example	Days									Menstrual Bleeding Episode (Yes/No)	Duration (days)
	1	2	3	4	5	6	7	8	9		
A	x	●	x	x	x	x	x	x	x	No	N/A
B	x	○	○	x	x	x	x	x	x	No	N/A
C	x	●	●	x	x	x	x	x	x	Yes	2
D	x	○	●	x	x	x	x	x	x	Yes	2
E	x	●		●	x	x	x	x	x	Yes	3
F	x	●	x	●	x	x	x	x	x	No	N/A
G	x	○	●	●	x	x	x	x	x	Yes	3
H	x	○		●	x	x	x	x	x	Yes	3
I	x	○			●	x	x	x	x	No	N/A
J	x	○	●	●		●	○	x	x	Yes	6
K	x	○		○	○	●	●	○	x	Yes	5

x = no spotting or bleeding; ○ = spotting; ● = bleeding; blank = missing; gray shading indicates menstrual bleeding episodes; N/A = not applicable

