8.3.2 Handling of Missing Data for the Primary Efficacy Endpoint(s)

The primary analysis will be based on observed cases only; missing data will not be imputed for the primary endpoint.

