8.3.4 Additional Analyses of the Primary Efficacy Endpoint(s)

The following sensitivity analyses for the primary efficacy endpoint will be conducted:

1. The menstrual cycle response for subjects who prematurely discontinue the study drug at or before Month 4 will be considered as missing. Multiple imputation (MI) approach will be used for the primary endpoint. Details regarding MI are in Section 8.2.
2. Subjects who prematurely discontinue study drug during the Treatment Period due to "lack of efficacy" or adverse event (AE) will be considered as non-responders, while subjects who discontinue study drug during the Treatment Period due to other reasons will be categorized as responders/non-responders in the same manner as done in the primary analysis.
3. All subjects who prematurely discontinue the study drug at or before Month 4 will be considered as non-responders and the primary analysis will be repeated. Subjects who discontinue after Month 4 will be categorized as responders/non-responders in the same manner as done in the primary analysis.
4. The difference between each elagolix group and placebo group in proportion of menstrual cycle responders will be analyzed using contrasts within a logistic

regression model with the responder/non-responder categorization as the dependent variable, treatment as the main effect, and baseline FG score ($< 8, \geq 8$) and baseline normal/obese status ($\text{BMI} < 30, \geq 30$) as the covariates. The proportion of menstrual cycle responders, difference in proportions between each elagolix group and placebo, and odds ratio with corresponding 90% confidence interval and P value will be presented.

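### Do Month 5 stops, scored on Months 2-5 in nearly every planned analysis, call for a further sensitivity analysis of the primary endpoint?

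*SAP*

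**What the plan says.** Protocol 7.3 calls a subject a responder if she has two or more normal cycles in the last four months of treatment, and leaves the details to the SAP. SAP 8.3.1 fixes that window at Months 3-6 for completers. For a stop at Month X it adds two rules: "where X is greater than or equal 4, this will be Month (X – 3) to Month X", and "where X is less than 4, this will be Month 1 to Month X".

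The primary analysis uses observed cases. SAP 8.3.2 says that "missing data will not be imputed for the primary endpoint", and SAP 8.2 adds that "OC will exclude values after a subject prematurely discontinues from study drug".

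SAP 8.3.4 lists four sensitivity analyses:

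1. Multiple imputation, where the response of subjects who stop "at or before Month 4 will be considered as missing".
2. Stops for an adverse event or lack of efficacy become non-responders, while "subjects who discontinue study drug during the Treatment Period due to other reasons will be categorized as responders/non-responders" as in the primary analysis.
3. All stops up to Month 4 become non-responders. For the rest, "Subjects who discontinue after Month 4 will be categorized as responders/non-responders in the same manner as done in the primary analysis".
4. A logistic "regression model with the responder/non-responder categorization as the dependent variable", with no new scoring rule.

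**The concern.** The sliding window runs through Month 5, but the cut-off in analyses 1 and 3 ends at Month 4. A subject who stops in Month 5, for example because she moves away, can be a responder on a cycle in Month 2. The same cycle would not count for a completer, and no planned analysis of the primary endpoint shows whether this affects a result.

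With 20 subjects per elagolix arm and 30 on placebo, one reclassified subject moves the rate by 1/20 = 5 percentage points or 1/30 = 3.3 points. SAP 8.3.3 calls each dose more efficacious or not at p of 0.1 or less, so one subject near that threshold could decide the call.

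**Working it through.** **Plan's own figure.** SAP 2.4 states at least 85% power for 10% vs 50%, 30 vs 20 subjects, two-sided alpha 0.05, Pearson chi-square. The pooled rate is (30 × 0.10 + 20 × 0.50)/50 = 0.26. The null SE is √(0.26 × 0.74 × (1/30 + 1/20)) = 0.1266. The alternative SE is √(0.10 × 0.90/30 + 0.50 × 0.50/20) = 0.1245. Power = Φ((0.40 − 1.96 × 0.1266)/0.1245) = Φ(1.22) = 88.9%. The claim reproduces.

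**Which stops are re-scored.** Applying SAP 8.3.1 and 8.3.4 by month of stop:

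| Stop in | Window | Analyses 1 and 3 | Analysis 2 | Analysis 4 |
|---|---|---|---|---|
| Months 1-3 | Month 1 to X | re-scored | AE / lack of efficacy only | as primary |
| Month 4 | 1-4 | re-scored | AE / lack of efficacy only | as primary |
| Month 5 | 2-5 | unchanged | AE / lack of efficacy only | as primary |
| Month 6 | 3-6, as completers | unchanged | AE / lack of efficacy only | as primary |

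Only Month 5 stops for other reasons have a window different from completers and keep it in all four analyses.

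**Can a score change?** Assume the 28-day months of Operations Manual 2.2 also apply to the endpoint. Months 2-5 are then Days 29-140 and Months 3-6 are Days 57-168. A normal cycle has 21-35 days between onsets. The SAP does not say how a cycle crossing a window edge is assigned, so two readings are used: the cycle lies wholly inside the window, or merely overlaps it.

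- Onsets on Days 30, 54 and 78, then no bleeding, give two cycles of 24 days. A Month 5 stop has 2 normal cycles. A completer has 0 (inside) or 1 (overlap). The score changes.
- Take all diaries with exactly two consecutive normal cycles and then no bleeding that respond at an end-of-Month-5 stop. Of these, 6,300 of 12,600 (50%, inside) or 5,985 of 18,360 (33%, overlap) would not respond as completers.
- With three consecutive normal cycles the share falls to 33% (inside) or 4% (overlap). With four it is about 4% and 0%.

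These are shares of possible patterns, not of patients. They show that a change needs cycling that begins early and then ceases.

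**How many subjects.** The documents give no dropout rate. Assume 10-30%, spread evenly over six months. Month 5 stops for any reason are then n × rate/6:

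- elagolix arm: 20 × 0.10/6 = 0.33 to 20 × 0.30/6 = 1.0
- placebo: 30 × 0.10/6 = 0.5 to 30 × 0.30/6 = 1.5
- all 130 subjects: 2.2 to 6.5

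Three conditions reduce these numbers: the reason is neither an adverse event nor lack of efficacy, the subject responds on Months 2-5, and she would not respond on Months 3-6.

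**Effect on the conclusion.** Unstratified Pearson test as a stand-in for the planned CMH test, placebo 3/30:

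| Elagolix responders | p |
|---|---|
| 10/20 (planned rate) | 0.0016 |
| 9/20 | 0.0045 |
| 8/20 | 0.012 |
| 6/20 | 0.071 |
| 5/20 | 0.156 |

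At the planned rates, losing one or two responders does not approach 0.1. Only a result already near the threshold changes.

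**What a fixed Months 3-6 analysis would measure.** The obvious remedy scores everyone on Days 57-168, uses no data after the stop and counts the rest as non-responders. A Month 5 stop then has at most three months of window instead of four. Consider women with perfectly regular cycles, every phase, with stops averaged over Days 113-140. The share who can respond changes as follows:

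| Cycle length | Inside: current → fixed | Overlap: current → fixed |
|---|---|---|
| 28 days | 100% → 52% | no loss |
| 30 days | 98% → 36% | 100% → 99% |
| 35 days | 79% → 11% | 100% → 89% |

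These women cycle normally throughout. Under the inside reading the losses come largely from the shortened window, so the analysis would not isolate the shift it was meant to test.

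**The case for a change.** The strongest case for acting is that the gap is real, appears by the text alone to be unintended, and is cheap to close: one paragraph and one derivation on diary data already collected. SAP 8.5.1 treats every stop before Month 6 as a non-responder and then repeats the analysis without discontinuers, but for the stricter complete-responder endpoint, so it does not test this one. Near the threshold one subject can matter. With assumed strata of 5/5/5/5 and 8/8/7/7, 6/20 vs 3/30 gives a stratified CMH p of 0.012-0.086 over all splits of responders. Removing one elagolix responder takes p above 0.1 in 99.7% of splits by weight.

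The reading of the text stands, and so does the arithmetic. But the example was chosen at the threshold, and it works in both directions: removing one placebo responder from 5/20 vs 3/30 lowers the unstratified p from 0.156 to 0.067. No direction of bias between arms is shown. Low cost is also a weak argument when the added analysis would confuse two effects.

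**Conclusion.** No change to the plan is needed. Scoring each subject on her last four months on drug is a fair trade-off. It keeps the window at a nominal four months for completers and Month 5 stops alike, and does not fail a subject merely because she left in Month 5. The price is that Month 2 can count for a few subjects. The rule is written down before analysis and applies equally to all arms. Stops up to Month 4, and all adverse-event and lack-of-efficacy stops, are already stress-tested. SAP 10.0 presents the study as proof of concept without Type I error control.

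The residual group is at most about one subject per elagolix arm under the assumed 10-30% dropout, before the three conditions apply. Its size will also be visible: SAP 6.0 tabulates treatment duration by arm with a 113-140 day interval, which is Month 5 on 28-day months, and SAP 5.0 tabulates reasons for discontinuation. If that interval is empty or nearly so, the question closes. If not, an analyst can move analysis 3's cut-off to Month 5 as a conservative bound when reporting, without amending the SAP.

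This conclusion rests on the assumed dropout range, its even spread over time and the 28-day month. Heavy dropout concentrated in Month 5 would weaken it, but nothing in the documents suggests that.
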